10.15 Confidentiality

The study records will be available for inspection by the FDA, the monitor/auditor, IRB and other regulatory agencies. Study-related records will be kept confidential, and to the extent permitted by applicable laws and/or regulations will not be made publicly available. In the case of the study results being published, the subjects' identities will remain confidential.

10.16 Posting of research study on web

A description of this clinical trial will be available on www.ClinicalTrials.gov, as required by U.S. Law.

11 Abbreviations and Terms

AE	Adverse Event
SAE	Serious Adverse Event
EC	Ethical Committee
IRB	Institutional Review Board
CRF	Case Report Form
VAS	Visual Analogue Scale

12 Appendices

Appendix I Study Flow Chart

Study Activities	Visit #0*	Visit #1***	Visit #2	Visit #3	Visit #4	Visit #5	Visit #6	Visit #7§	Visit #8§	Visit #9§§
	Pre-Tx	Tx #1 Up to 7 days after Visit 0	Tx #2 4-6 WKS POST Tx1	Tx #3 4-6 WKS POST Tx2	Tx #4 4-6 WKS POST Tx3	Tx#5 -6 WKS POST Tx4	Tx #6 4-6 WKS POST Tx5	FU #1 1M±7 D FU	FU #2 3M±7 D FU	FU #3 6M±7 D FU
Qualify for study: Informed Consent, Eligibility assessment, Demographic information, Medical history & treatment related medical examination	X									
Test spots**		X Pre-Tx								
Photographs	X			X Pre-Tx			X Pre-Tx	X	X	X
Treatment		X	X	X	X	X				
Immediate and short term response		X	X	X	X	X	X			
Hair Count by study personnel	X			X			X	X	X	X
Hair Count by blinded evaluators (to be conducted post study)	X							X	X	X
Subject's comfort assessment		X	X	X	X	X				
Subject's improvement/satisfaction				X			X	X	X	X
Adverse events recording		X	X	X	X	X	X	X	X	X
Study termination										X

* Visit #0 includes various screening activities and explanations to the candidate regarding the evaluation; should the subject sign the Informed Consent Form, complete the test spot procedure and undergo treatment during Visit #0, it will effectively become merged with Visit #1.

** Test spots should be performed prior to Tx #1 and with any treatment parameter alternation later on in treatment regime.

*** An Intermediate Safety report will be performed following Tx #1.

§ A Hair Removal report will be performed following FU #1 and FU #2 of 1M ±7D; 3M ±7D.

§§ A Permanent Hair Reduction report will be performed following FU #3 of 6M±7D.

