4.1 Primary Effectiveness Endpoints

- Hair count reduction, as calculated from photographs and defined as (count-baseline)/baseline*100; 3 months following the last treatment FU2 (hair removal).

- Hair count reduction, as calculated from photographs and defined as (count-baseline)/baseline*100; 6 months following the last treatment FU 3 (permanent hair reduction).

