7.2.1.2 Hair reduction assessment

Hair counts will be accomplished by analysis of photographs. The original image of the photographs will be saved and archived in its original form by the site and a copy will be sent to the sponsor. The image will be enlarged to a uniform size to facilitate counting and the file shall be saved (locked) into a PDF format.

At baseline, immediately before treatment 3 and 6, 1M FU1, 3M FU2 and 6M FU3, a copy of the image shall be printed. Each image will be reviewed by the investigator or his/her designees. Additional copies of baseline, 1M FU1, 3M FU2 and 6M FU3 will be sent to two other reviewers who are blinded to the treatments. The reviewer will mark each hair identified with a red pen, and each of these marks will be tallied to obtain hair count. For a detailed hair count explanation please refer to section 7.4.2.2.

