7.2.2.2 Level of improvement and satisfaction

Subject's Improvement and Satisfaction with treatment will be recorded by a 5-point Scale: 1=None; 2=Slight; 3=Moderate; 4=Good; 5=Very Good.

Table 1– Clinical Evaluation Tools

Claim/task	When to conduct?	Tool
Photography	Baseline, immediately before treatments 3, 6, 1M±7D FU1, 3M±7D FU2 and 6M±7D FU 3	Standardized digital photographs
Hair count by single study personnel	Baseline, immediately before treatments 3, 6, 1M±7D FU1, 3M±7D FU2 and 6M ±7D FU3	Standardized digital photographs
Hair count by blinded reviewers	Baseline, 1M ±7D FU1, 3M ±7D FU2 and 6M ±7D FU3	Standardized digital photographs
Immediate and short term response	Immediately following treatments 1-6	Examination of skin in the treated area based on 5 level scale
Subjects comfort assessment	Immediately following treatments 1-6	VAS
Subjects improvement/satisfaction assessment	Treatments 3, 6, 1M ±7D FU1, 3M ±7D FU2 and 6M ±7D FU3.	5 point scale
Safety	Throughout study	Examination of skin in the treated area, interview subjects

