8.3 Study Analysis

The objective of this clinical study is to evaluate the safety of hair removal and to verify hair removal and permanent hair reduction using the Versa HR 690 nm applicator assessed by hair counts. For this purpose an average of hair count of 2 blinded reviewers will be done at baseline, following treatments, and at follow up visits. In case of a big discrepancy between 2 blinded reviewers, the hair count will be redone by a third blinded evaluator.

An intermediate safety report will be produced based on analysis of data collected post treatment number one of all the enrolled subjects. A Hair Removal report will be produced based on analysis of data collected at the three-month follow-up visit and a Permanent Hair Reduction report based on the analysis of data collected at the six-month follow-up visit will be the final report. The interim reports will not affect the continuation of the study. The study will regardless of the interim report results, be finalized according to this protocol.

The study reports will provide information for use in research & development, and future planned study. All statistical tests will be two-sided. The level of statistical significance for effectiveness analyses is five percent for all tests of differences. Paired t-test and/or Wilcoxon signed rank test will be used to compare the evaluations at the baseline and follow up sessions. Descriptive statistics and correlations between variables will be performed.

Safety: Adverse events reported will be listed, documenting course, outcome, severity, and possible relationship to the treatment.

9 Adverse Events

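### Blinded hair counts are scheduled only after the study, yet a seemingly interim report covers the 3-month primary endpoint, and the plan does not say which counts that report uses

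*Combined protocol and SAP*

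**What the plan says.** **Endpoint.** Section 4.1 makes the percent change in hair count from baseline a primary endpoint at FU2 ("3 months following the last treatment FU2 (hair removal")) and again at FU3. It does not name the counter.

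**Source of the counts.** Section 8.3 does: "For this purpose an average of hair count of 2 blinded reviewers will be done at baseline, following treatments, and at follow up visits". A third blinded evaluator recounts when the two disagree widely.

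**Reports.** Section 8.3 plans a safety report after the first treatment, then "A Hair Removal report will be produced based on analysis of data collected at the three-month follow-up visit", then a Permanent Hair Reduction report on the six-month data, which it calls final. It uses the plural when it speaks of interim reports, and says the study runs to its end whatever they show. The Appendix I footnote agrees on the order: "A Hair Removal report will be performed following FU #1 and FU #2".

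**Timing of the blinded counts.** The Appendix I row is "Hair Count by blinded evaluators (to be conducted post study"), marked for baseline, FU1, FU2 and FU3. Study termination is marked at FU3. Section 7.2.1.2 says "Additional copies of baseline, 1M FU1, 3M FU2 and 6M FU3 will be sent to two other reviewers who are blinded to the treatments", but does not say when those images are read.

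**Site counts.** Section 7.2.1.2 also says "Each image will be reviewed by the investigator or his/her designees". Table 1 (section 7.2.2.2) lists "Hair count by single study personnel" at baseline, before treatments 3 and 6, and at all three follow-up visits.

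**The concern.** The study has one arm, and each subject is compared with his or her own baseline. Without a concurrent control, a counter who knows that an image comes from after treatment can shift the primary result directly, and no comparison group absorbs the shift. Blinded reading of photographs is the main protection against this, and is what lets the design be called blinded.

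As scheduled, that protection arrives after the 3-month report appears to be due. A team following the flow chart and the report sequence would have only site counts to analyse. A team that instead sent the FU2 images to the blinded reviewers early would depart from the flow chart. It would then read FU3 later, as a separate batch recognisable as FU3. The plan gives no rule for choosing between these courses, although the choice fixes the data source of a primary endpoint.

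**Working it through.** The plan states no figure for this point, so there is none to reproduce. The check sets the rules side by side, works out the visit timing, and asks what can be said about bias.

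**1. The rules together**

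| Rule | Where | Consequence |
|---|---|---|
| FU2 hair count is a primary endpoint | 4.1 | The Hair Removal report carries a primary result |
| Analysis uses the mean of two blinded reviewers | 8.3 | The report needs blinded FU2 counts |
| Report follows FU1 and FU2; the six-month report is final; earlier ones are interim | 8.3, Appendix I | The report reads as issued while FU3 is still pending |
| Blinded counting is done post study; termination is at FU3 | Appendix I | No blinded FU2 counts exist until FU3 is complete |
| Site personnel count at FU2 | 7.2.1.2, Table 1, Appendix I | These are the only FU2 counts scheduled by then |

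The second, third and fourth rows cannot all be met if the report is interim in the ordinary sense.

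**2. The time gap**

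Inputs: six treatments, hence five intervals of 4 to 6 weeks; FU2 at 3 months and FU3 at 6 months after the last treatment, each ±7 days (sections 5.1 and 7.1). One month is taken as 30.4375 days.

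- Last treatment, from the first: 5 × 28 = 140 days, to 5 × 42 = 210 days.
- FU2: 140 + 91.3 = day 231, to 210 + 91.3 = day 301.
- FU3: 140 + 182.6 = day 323, to 210 + 182.6 = day 393.
- FU2 to FU3 for one subject: 3 × 30.4375 = 91.3 days. With both windows at their extremes, 91.3 − 14 = 77 days to 91.3 + 14 = 105 days, or about 2.5 to 3.5 months.

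A report issued when the last subject completes FU2 would precede the end of the study by about that interval. With staggered enrolment some early subjects may have passed FU3, but the study would not be over.

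**3. Are the site counters unblinded?**

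The documents do not say so outright. Section 7.2.1.2 contrasts them with two other reviewers who are blinded. The visit date is written on the template frame that is photographed (sections 6.2.2 and 7.4.2.2), and no masking is described for site staff. The inference is well supported, but it remains an inference.

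**4. Size of any bias**

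Suppose the baseline count b is correct and e hairs are missed at FU2. The percent change then moves by 100 × e / b points towards a larger reduction. If the same fraction is missed at both visits, the percent change does not move, so only a differential miss matters. The documents give no value for e and no typical b; section 5.2.1 requires only more than 15 hairs in the count site. As pure illustration, with an assumed b of 40 and an assumed e of 2 to 6, the shift is 2/40 = 5 points to 6/40 = 15 points. These values show sensitivity; they do not estimate what would happen here.

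**The case against.** A reader might infer that the Hair Removal report can rest only on unblinded site counts. The documents do not support that. Nothing says the report uses site counts, and section 8.3 points to blinded counts for the analysis. The sponsor might equally read the FU2 images early or hold the report until the reading is done.

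Nor is an issue date given. Both statements about the report say what data it uses or which visits it follows, and neither sets a latest date. A report written after the post-study reading would satisfy both sentences taken alone. That it comes before FU3 is inferred from the word interim and from the six-month report being the final one.

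A reader might also infer that the 3-month primary endpoint would be settled permanently by site counts. That does not follow either. Blinded counts of the baseline and FU2 images are planned in any case, and the interim reports do not decide whether the study continues. At worst, a provisional conclusion would come out ahead of the blinded one.

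Finally, a single post-study batch does not by itself hide the visit from readers, because the date is on the photographed frame. Section 6.2.1 removes identifying details but does not mention the date.

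These points limit how far the concern goes. They do not remove the conflict: the natural reading of the report sequence still needs blinded FU2 counts before the flow chart produces them.

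**Conclusion.** The point holds as a conflict over timing and data source for one of the two primary endpoints. Blinded counting is placed after the study, the analysis is to use blinded counts, and the 3-month report reads as interim. The plan does not say which counts that report uses. This is more than missing detail, because stated rules pull against each other.

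The risk is that the 3-month efficacy conclusion is first reported from unblinded counts in a study with no concurrent control. This rests on two inferences: that the report precedes the end of FU3, and that site counters know the visit. The gap is about 91 days per subject (77 to 105). The bias has no derivable size. The FU3 result, reported last, is not exposed to this conflict. The wording should be settled before any FU2 hair-count analysis.

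**What to change.** **Wording.** State in section 8.3 and in the Appendix I footnotes that the Hair Removal and Permanent Hair Reduction efficacy results use only the two-reviewer blinded counts, with the third blinded evaluator where 8.3 calls for one.

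**Timing, simplest option.** Keep one post-study blinded reading. Present baseline, FU1, FU2 and FU3 images in mixed order, with the visit date on the template frame hidden from the readers. Issue the Hair Removal efficacy result after that reading. Limit any earlier 3-month report to safety and subject-reported data.

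**Cost.** Text changes, masking of the date on the images, and a Hair Removal efficacy report about three months later (77 to 105 days per subject). No extra visits or readers are needed.

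**If the earlier report is needed.** Amend the post-study note in Appendix I so that baseline, FU1 and FU2 images are read blinded before the report. Later, re-read the baseline images mixed with the FU3 images, so that FU3 is not an identifiable batch compared with counts made months before. The cost is a second baseline reading: with one count image per subject (an assumption), 120 × 2 reviewers = 240 further image readings, and more if subjects have several count sites.
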